A computer-generated randomization using a 1:1 allocation ratio in permuted blocks of 8 will be developed by the study statistician uninvolved with data collection and administered by the research pharmacist at Wake Forest School of Medicine. The 'blockrand' package in R will be used by the study statistician. The randomization will be stratified based on study recruitment site, concurrent use of a serotonin-norepinephrine reuptake inhibitor, and chronic low- or high-dose opioid therapy. Allocation will be conducted by the research pharmacist and will occur after consent and completion of the first visit. At all times, the allocation assignment will be concealed from the study coordinator and other investigators who manage participant recruitment and follow-up. Allocation concealment is maintained using a centralized pharmacy administration of study drug. Both study agents are designed to look identical to each other to maintain blinding.

11. Sample size

To calculate the statistical power for our analytical strategies, we simulated scenarios for which we instilled known relationships between the random effects of change models as well as a range of predictors of those parameters that were themselves correlated. A sample size of 250 was to determine to provide substantial power (> 90%) to detect clinically significant differences between a null model versus a demographic/perioperative + psychosocial predictors model using a likelihood ratio test. An example of the expected differences is displayed (left) that illustrates a three-way interaction between treatment (Placebo vs Gabapentin), cognitive-affective style (Optimist vs Catastrophizing), and pupil size (Low, Mid, High).

12. Framework

Superiority testing will be used to examine difference between the effect of treatment alone on the change process in pain after surgery and the effect of treatment as interacting with preferred cognitive style and pre-surgery pupil responses to painful stimuli.

13a. Information on interim analyses

There are no planned interim analyses.

13b. Any planned adjustment of the significance level due to interim analysis

None.

13c. *Details of guidelines for stopping a trial early*

There is no plan to stop the trial early aside from recommendations based on unanticipated serious adverse events by the DSMB.

14. *Timing of final analysis*

Table 1. Timing of study measures

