Study period	Screen	Baseline	In hospital	Daily diaries	Follow up 1	Follow up 2	Phone	Orthopaedic clinic visits
Visit number	0	Visit 1			Visit 2	Visit 3		
Week		-4 to -2*	0-3 days	0-8	8	26	12,16,20,52	2, 6, 12-16, 26, 52
Informed consent		X						
Demographic		X						
Medical/surgical history		X						
Questionnaires		X			X	X		
Pain testing & pupillometry		X						
Randomisation		X						
Study drug dispensing		X						
In hospital pain/medication data & disposition			X					
Daily diary & accelerometry		X		X				
Phone assessment of pain, medication use, function							X	
Joint function								X

*Study medication begins at -2 weeks and continues until 3 weeks after surgery

Final analysis of the gabapentin vs placebo comparison with and without inclusion of interactions with preferred cognitive style and pre-surgery pupil responses to pain will take place when all patients have completed the 12-month follow-up and data for the primary endpoint have been cleaned, which occurred in May 2022. Results were anticipated to be posted by Jan, 2023, but complexities associated with generation of a novel psychologic construct from the final dataset and defining parameters for pupil assessment prevented completion of the primary analysis until Mar, 2023.

15. *Timing of outcome assessments*

The schedule of study procedures is provided in the protocol and summarized in the table below.

Section 4: Statistical Principles

16. *Level of statistical significance*

All applicable statistical tests will be 2-sided and will be performed using a 5% significance level.

17. *Adjusting for multiplicity*

The primary analysis involves a single model-based inference that will be interpreted at the 5% threshold of statistical significance. If the primary analysis is significant, each main factor, all two way interactions, and the three way interactions will be evaluated and each will be interpreted at the 5% level of significance with no adjustments made for multiplicity.

18. *Confidence intervals*

All confidence intervals presented will be 95% and two-sided.

19a. *Definition of adherence to the intervention and how it is assessed*

Compliance is assessed based on the number of daily diary entries after hospital discharge. It is defined as:

$$\% \text{ compliance} = (\text{number of entries}/\text{number of days entries were to be completed}) * 100\%$$

19b. *How adherence will be presented*

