The primary analysis will model trajectory of recovery of daily worst pain ratings and examine several sources of influence on this recovery. Sometimes referred to as mixed-effects models, or hierarchical linear models, growth curve modeling allows specification of a change trajectory that is unique to each individual. The nature of the common form of changes in daily pain will be modeled using a curvilinear form (e.g., polynomial regression). Through the use of fixed and random effects, variations in intercepts (i.e., levels of pain on day of discharge) and slopes (i.e., change in daily pain over time) can be examined using the pre-specified influences outlined below. To model individual pain trajectories, several model form candidates will be examined with the best fit determined using a Bayesian Information Criterion. These model forms will include linear, quadratic, cubic, and log(time), and each of these model candidates will be employed that reflect a fundamental change in trajectory that occurs during the observation period. Based on preliminary data it is highly likely that a log(time) form will be chosen.^{1,2}

To examine the proposed hypotheses, several key sets of predictors will be specified including patient characteristics, operative characteristics, cognitive style, randomized treatment assignment, and pre-operative pupil diameter response. Each of these predictors are described below:

Patient characteristics: To adjust the associations for individual age and sex will be entered into the model.

Operative characteristics: To adjust the associations for any subtle differences in medical care, study site, and surgery type (hip or knee arthroplasty) will be entered into the model.

Cognitive style: Multidimensional scaling of the pre-operative questionnaires will be conducted to create a unidimensional scale that represents a broader spectrum of cognitive style that ranges from optimism/acceptance of pain to catastrophizing. This novel predictor will be examined for reliability and correlations with the original scales. If insufficient reliability ($\alpha < 0.70$) or construct validity ($r < |0.40|$) with the original scales cannot be obtained, the analysis will proceed using the originally scaled catastrophizing predictor.

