Pupil diameter: Pupil recordings will be conditioned to remove artifacts (e.g., blinks), saccades, and deviations from central gaze that might bias recordings. A response window with appropriate lag reflecting delayed onset of pupil response due to physiological delays will be used to define change in diameter to each stimulus as previously reported.¹⁷ Two pupil measurements will be estimated from the session data, the mean pupil diameter during baseline (i.e., pre-stimulus) and the modeled response to pupil to 50-degree stimulus.

Gabapentin: Randomized treatment assignment of either gabapentin or placebo will be a fundamental predictor of trajectory.

These individual predictors sets will then be used to test the primary hypothesis that gabapentin alters time course of recovery after arthroplasty in a manner dependent on its interaction with preferred cognitive style and pre-surgery pupil diameter. The primary statistical inference will be the difference in the likelihood ratio between two nested models using a chi-square test with K degrees of freedom (i.e., K being the difference in the number of parameters between the two models). The first model (i.e., null model) will consist of the pain trajectory model with the addition of patient characteristics and operative characteristics. The second nested model will add medication assignment (gabapentin versus placebo), cognitive style (catastrophizing \leftrightarrow optimism latent score), and resting pupil diameter, and all two-way interactions and three-way interaction between these 3 predictors (i.e., 3 two-way, and 1 three-way interaction for both intercept and slope parameters) from the first nested model. This approach allows a single likelihood ratio test of the primary hypothesis and will be interpreted using a two-tailed hypothesis test using $p < 0.05$. A statistically significant difference in the likelihood ratio test will be interpreted as evidence to support the primary hypothesis in that the interaction of these predictors impacts some aspect of the change process beyond that of the basic model. We have planned several sensitivity analyses using multiple imputation to account for missing data.

Several exploratory secondary analyses of the data set:

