The assumptions underlying parametric modeling will be evaluated using regression diagnostic procedures and histograms of residuals.

27d. Alternative methods to be used if distributional assumptions do not hold for primary and secondary analyses

If necessary, the primary outcome distribution will be log transformed to satisfy assumptions. For secondary outcomes, the generalized linear model allows the specification of an array of distributions (e.g., normal, binomial, gamma) with corresponding link functions (e.g., log).

27e. Planned sensitivity analyses

Four sensitivity analyses will be performed to evaluate the robustness of the trajectory analysis to the primary and secondary analyses. These are to include multiple imputation for missing data, to include baseline measures of primary and secondary outcomes as predictors in the trajectory models, to include monthly through 6 months and the 12-month daily diary data and to include patient race and surgeon as other causes of variability in trajectory in the primary analysis.

27f. Planned subgroup analyses

No subgroup analyses are planned.

28. Missing data – reporting and assumptions/statistical methods to handle missing data

Multiple imputation will be used to account for embedded missing data in daily diary entries. The autocorrelation of each time-series for each individual along with baseline predictors will be used in conjunction with the MICE algorithm to estimate $m = 20$ imputations. These imputations will then be re-analyzed using the primary model with Rubin's rules used to pool the estimates of model parameters.

29. *Details of any additional statistical analyses required e.g., complier-average causal effect analysis.*

None

30. *Harms*

The number (and percentage) of patients experiencing each AE/SAE will be presented for each treatment arm categorized by severity. For each patient, only the maximum severity experienced of each type of AE will be displayed. The number (and percentage) of occurrences of each AE/SAE will also be presented for each treatment arm. No formal statistical testing will be undertaken

31. *Statistical Software*

The analysis will be carried out using R version 4.1.2

32. *References*

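### SNRI use is a randomization stratum but is named in no primary, secondary or sensitivity model, and the SAP gives no reason; the likely effect is small and the remedy cheap

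*SAP*

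**What the plan says.** **Randomization.** SAP section 10 describes permuted blocks with allocation "stratified based on study recruitment site, concurrent use of a serotonin-norepinephrine reuptake inhibitor, and chronic low- or high-dose opioid therapy".

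**Primary models.** Section 27a/27b fixes the covariates in two sets. For patient characteristics, "individual age and sex will be entered into the model". For operative characteristics, "study site, and surgery type (hip or knee arthroplasty) will be entered into the model". These sets define the smaller model: "The first model (i.e., null model) will consist of the pain trajectory model with the addition of patient characteristics and operative characteristics". The larger model adds treatment, cognitive style, resting pupil diameter and all their interactions, on intercept and slope. One likelihood ratio test compares the two.

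**After the joint test.** Section 17 continues: "If the primary analysis is significant, each main factor, all two way interactions, and the three way interactions will be evaluated", each at 5% without multiplicity adjustment.

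**Sensitivity analyses.** Section 27e plans "to include baseline measures of primary and secondary outcomes as predictors in the trajectory models" and "to include patient race and surgeon as other causes of variability in trajectory in the primary analysis". SNRI use is in neither.

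**Reasons given.** The SAP 2.2 appendix argues that adjusting for preoperative pain, activity, disability or opioid use would weaken the independent effect of the cognitive construct. It does not mention SNRI use.

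**The concern.** Of the three stratification factors, only site enters the primary models. The opioid stratum has a stated rationale in substance, and baseline opioid use can enter a section 27e sensitivity analysis as a baseline outcome measure. SNRI use has neither.

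Two things follow:

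- **Treatment terms.** Stratified allocation balances SNRI use between arms, so leaving it out causes no bias. The model does not remove the variance the stratum explains, so standard errors are a little too large and tests slightly conservative.
- **Pupil main-effect terms.** Pupil diameter is not randomized, so stratified allocation does not balance SNRI use across pupil sizes. Sections 7 and 8 of the SAP treat the pupil as a measure of locus coeruleus activity and describe that nucleus as acting through norepinephrine release. On that rationale, a norepinephrine reuptake inhibitor could plausibly relate to both pupil size and pain. Part of an apparent pupil effect could then belong to SNRI use, and no named model would show it.

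**Working it through.** **1. Stratification factors against model terms**

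| Factor (section 10) | Primary models (27a/27b) | Sensitivity (27e) | Reason for omission |
|---|---|---|---|
| Site | yes | – | – |
| Opioid therapy | no | indirectly, via baseline outcome measures | SAP 2.2 appendix, in substance |
| SNRI use | no | no | none in this document |

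The exploratory trajectory models are to follow a similar approach to the primary analysis and do not name SNRI use either. It could enter through sets whose content is not listed: the medications in the baseline table (section 25a), the imputation model ("along with baseline predictors will be used in conjunction with the MICE algorithm", section 28), or the preoperative patient characteristics in exploratory item 6.

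**2. Inputs for the size**

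From the SAP: 250 patients; a 5% level; and 7 added terms (3 main effects, 3 two-way, 1 three-way) on intercept and slope. With a single time term such as log(time), this gives 7 × 2 = 14 degrees of freedom and a critical value of 23.68.

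Assumed, because the SAP gives no prevalences or associations: stratum prevalence p of 5-10%, pupil shift d of 0.5-1 SD, pain shift e of 0.3-0.5 SD, no true pupil effect, and a shift in the intercept only. Write v = p(1 − p).

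**3. Precision of the treatment terms**

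R² = v·e² / (1 + v·e²); standard-error inflation = 1/√(1 − R²); equivalent sample size = 250/(1 − R²).

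- Low case (p = 0.05, e = 0.3): v = 0.0475, R² = 0.4%, inflation 1.002, equivalent size 251.
- High case (p = 0.10, e = 0.5): v = 0.09, R² = 2.2%, inflation 1.011, equivalent size 256.

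Standard errors are 0.2-1.1% too large, worth 1-6 patients. A nominal 5% treatment test has a true level of 2[1 − Φ(1.96/√(1 − R²))], about 4.95% in the low case and 4.75% in the high case.

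**4. Confounding of the pupil main effect**

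Spurious correlation r = v·d·e / √[(1 + v·d²)(1 + v·e²)]; noncentrality = 250·r²/(1 − r²).

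- Low case (d = 0.5): r = 0.007125/√(1.011875 × 1.004275) = 0.007; noncentrality 0.012.
- High case (d = 1): r = 0.045/√(1.09 × 1.0225) = 0.043; noncentrality 0.455.

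| Case | Joint test, 14 df | Pupil main effect, 1 df |
|---|---|---|
| No confounding | 5.0% | 5.0% |
| Low | 5.0% | 5.1% |
| High | 6.1% | 10.4% |

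The 1-df column applies when the joint test is significant for other reasons. That is realistic: the SAP 2.2 appendix cites a positive correlation of catastrophizing with pain, and cognitive style is in the same joint test.

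**5. Does the covariate repair it?**

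A simulation of 8000 runs with 250 patients used patient-level intercepts and slopes rather than the full mixed model. In the high case the joint test rejected in 6.3% without the stratum covariate and 5.1% with it (Monte Carlo standard error about 0.24 points).

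**The case against.** The strongest case against the point has five parts.

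- **The effect is small and every numerical input is assumed.** This stands. The SAP documents no SNRI prevalence and no link of SNRI use to pupil size or pain. Larger figures need stronger inputs: 40% prevalence with a 1 SD pupil shift and a 0.5 SD pain shift gives 13.5% for the joint test. Nothing in the SAP supports such values, so a reader should not infer that the primary test is seriously inflated.
- **Treatment is protected by design.** This stands. A reader might infer that the gabapentin comparison is biased. Stratified allocation rules that out; only a slight loss of precision remains.
- **A rationale may exist elsewhere.** The SAP rests on protocol 7.0, and SAP 2.2 removed adjustments because they were in neither the protocol nor the funding application. The complaint of a missing reason is therefore limited to this document. The SAP nevertheless lists its own covariates and sensitivity analyses, so the omission is visible in what it fixes.
- **A main-effect covariate does not fully answer the concern.** This stands. The hypothesis is about treatment interactions. If SNRI use modified the gabapentin effect, the treatment-by-pupil terms would stay exposed after adding SNRI use alone.
- **The change may come too late.** Section 14 dates completion of the primary analysis to March 2023. Altering the models after that would be a post hoc covariate change, which limits the remedy.

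A reader might also infer that both missing strata are equally unexplained. The SAP 2.2 appendix does not support that for opioid therapy.

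**Conclusion.** The point holds in a limited form. SNRI use is a stratification factor that no primary, secondary or sensitivity model names, and this document gives no reason. The textual finding is firm; its numerical consequence is not.

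Under the assumed 5-10% stratum, the cost to the treatment terms is negligible and the joint test is barely affected. The more noticeable effect is on the pupil main effect once the joint test has been passed for another reason, where a nominal 5% test could reject in up to 10.4%. That figure rests on the high-case shifts in pupil and pain, on no true pupil effect, and on an intercept-only shift treated at patient level.

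The omission does not invalidate the primary analysis. It should be corrected because it is cheap to do so and because a pupil finding would otherwise be open to an obvious question that no named analysis answers.

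**What to change.** - **If the primary analysis has not been run:** add SNRI use, as recorded for randomization, as a covariate on intercept and slope in both nested models. The term is in both, so the degrees of freedom of the test do not change (14 with a single time term). The variable already exists because allocation needed it.
- **If it has been run:** keep it as it is and report one labelled sensitivity analysis with SNRI use added to both models. The cost is one extra model fit.
- **For the treatment-by-pupil terms:** an SNRI-by-treatment term can be added in that sensitivity analysis, since the main-effect covariate does not protect them if SNRI use modifies the gabapentin effect.
- **If SNRI use was left out on purpose:** state the reason in section 27b.

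The opioid stratum is not part of the required change. Adjusting for it is a trade-off under the reasoning in the SAP 2.2 appendix.

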8. *Objectives*

The objective of this research study is to better understand patterns of recovery after total hip arthroplasty (THA) and total knee arthroplasty (TKA). The study will evaluate how pain, pupil diameter as a measure of LC activity and cognitive (i.e., thinking style) determine patterns of recovery, and the study will evaluate the efficacy of gabapentin versus placebo for improving recovery after surgery.

Research hypothesis: The null hypothesis (H_0) is that modeled trajectory of change in pain intensity report after THA and TKA does not differ between oral gabapentin and placebo in a manner dependent on its interaction with preferred cognitive style and pre-surgery pupil resting diameter. The alternative hypothesis (H_1) is that there is a difference between the two groups which is dependent on these interactions. The null hypothesis will be tested through contrasting the fit of a null model (m_0), with only change parameters and prognostic covariates, and the full model (m_1), which includes all of the predictors in null model with the addition of randomized treatment group, cognitive style, resting pupil diameter, and all two and three-way interactions. The difference in fit will be evaluated using a likelihood ratio test, as further described below.

$$H_0: -2 * (\loglik[m_0] - \loglik[m_1]) = 0$$

$$H_1: -2 * (\loglik[m_0] - \loglik[m_1]) > 0$$

Study objective: The primary objective is to determine the effectiveness of oral gabapentin to speed recovery from pain, as measured by growth curve modeling, after THA or TKA and how this effectiveness is modified by preferred cognitive style and pre-surgery resting pupil diameter.

Secondary objectives are planned to explore the role of these factors interact to predict other outcomes from surgery, including speed of gain in activity, assessed by actigraphy, speed recovery from self-assessed disability, and time to cessation of opioid use; to explore whether change in pupil diameter to acute experimental pain explains additional variance in a 4-way interaction compared to the 3-way interaction in the primary analysis.

Section 3: Trial Methods

9. Trial design

[figure not shown]
The trial is a two-center, randomized, double-blinded, parallel-group, placebo-controlled trial. Treatment allocation is a 1:1 ratio. Patients are randomized to either gabapentin or placebo control.

10. Randomization

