There is a large literature demonstrating a positive correlation between the extent of pain catastrophizing with pain, disability, and opioid use and a negative correlation with activity. Since the cognitive construct to be used in both the primary analysis and the secondary analyses is derived from the pain catastrophizing instrument, adjustment of modeled trajectories by preoperative pain, activity disability, and opioid use would be expected to diminish the independent effect of the cognitive construct in these analyses. The adjustments in modeling using these preoperative variables were intended as sensitivity analyses rather than testing the primary and secondary hypotheses. This mistake was identified and this amendment was prepared and submitted prior to performing analyses using these adjustments.

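### The primary likelihood ratio test can be significant through cognitive style alone, yet section 27 reads it as support for the gabapentin interaction hypothesis; section 11 does not establish that its >90% is power for that hypothesis

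*SAP*

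**What the plan says.** Section 8 states the alternative hypothesis twice. In words: "The alternative hypothesis (H_1) is that there is a difference between the two groups which is dependent on these interactions". In symbols, it is that minus twice the log-likelihood difference between m_0 and m_1 exceeds zero.

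Section 27a/27b defines the two models. For m_0: "The first model (i.e., null model) will consist of the pain trajectory model with the addition of patient characteristics and operative characteristics". The larger model, m_1, then brings in treatment, style and resting pupil size, together with every interaction among them, and these interactions act on both intercept and slope. The conclusion follows from that one test: "A statistically significant difference in the likelihood ratio test will be interpreted as evidence to support the primary hypothesis in that the interaction". The sentence ends by claiming that some part of the trajectory is altered.

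Section 11 says that a likelihood ratio test on 250 patients has "substantial power (> 90%) to detect clinically significant differences between a null model versus a demographic/perioperative + psychosocial predictors model". The sentence after it, on treatment, style and pupil size, reads "An example of the expected differences is displayed (left) that illustrates a three-way interaction".

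Section 17 adds that, after a significant primary test, the main factors and the interactions are each examined at 5% without adjustment.

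The appendix (SAP 2.2) says of cognitive style: "There is a large literature demonstrating a positive correlation between the extent of pain catastrophizing with pain, disability, and opioid use". Adjustment for preoperative values was removed because it "would be expected to diminish the independent effect of the cognitive construct in these analyses".

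**The concern.** The worded H_1 is about gabapentin against placebo and how that difference varies with style and pupil. The test compares m_0 with a model holding three main effects and four interactions, and m_0 contains none of the seven. A rejection says that at least one of these terms matters, not which one.

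One of them, cognitive style, is expected by the SAP itself to be related to pain. A significant result could therefore mean only that catastrophizing patients report more pain, while section 27 would have it reported as support for the interaction hypothesis. The same gap affects section 11: power for a comparison that includes style is not, by that fact, power to detect gabapentin interactions.

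**Working it through.** **The plan's own figure.** The >90% cannot be reproduced. Section 11 gives no effect sizes, variances, correlations or degrees of freedom for its simulation. What can be checked is how the section 27 test behaves when gabapentin does nothing.

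**Inputs from the SAP.** N = 250 (section 11); 5% level (section 16); m_0 and m_1 (sections 8 and 27).

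**Degrees of freedom.** m_1 adds 3 main effects + 3 two-way + 1 three-way = 7 terms. Taking all of them to act on intercept and slope, a linear or log(time) form gives 7 × 2 = 14. Section 27 thinks log(time) highly likely. Of the 14, style, pupil and style × pupil take 3 × 2 = 6 and involve no treatment. The other 8 are treatment (2) and the three gabapentin interactions (3 × 2 = 6). If every change parameter is interacted, a quadratic form gives 7 × 3 = 21 and a cubic form 7 × 4 = 28.

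**Assumptions.** Gabapentin has no effect, there are no interactions, and style has correlation r with the patient's pain intercept only. Intercept and slope errors are uncorrelated. The values of r are a range, not taken from the SAP.

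**Formula.** Noncentrality λ = −250 × ln(1 − r²). The rejection rate is the probability that a noncentral chi-square on 14 df exceeds the 5% critical value, 23.68.

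| r | λ | Rejection, 14 df | Simulated, 14 df | Simulated, 6-df gabapentin interactions |
|---|---|---|---|---|
| 0 | 0 | 5% | 6.3% | 6.0% |
| 0.1 | 2.51 | 12.6% | 14.3% | 5.9% |
| 0.2 | 10.21 | 48.3% | 51.8% | 6.4% |
| 0.3 | 23.58 | 90.8% | 92.7% | 6.3% |
| 0.4 | 43.59 | 99.8% | 99.9% | 6.4% |

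The simulation used 4,000 trials per r, complete balanced data, and a bivariate regression of intercept and slope on four covariates and the seven terms. The excess over 5% in the null cells is the small-sample behaviour of the maximum-likelihood test. A second simulation, with an intercept–slope error correlation of −0.3 and a style–pupil correlation of 0.2, gave 57% at r = 0.2 and 95% at r = 0.3 on 14 df. The 6-df test again stayed near 6%.

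**Where style alone reaches 90%.** On 14 df the required λ is 23.02. Then 23.02/250 = 0.0921, r² = 1 − exp(−0.0921) = 0.088, and r = 0.297. On 21 df λ = 26.60 and r = 0.318; on 28 df λ = 29.60 and r = 0.334.

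**What section 11 could mean.** Read literally, its comparison adds demographic, perioperative and psychosocial predictors and names neither treatment nor pupil. Read as shorthand for m_0 against m_1, which the adjacent three-way example favours, it is the 14-df test. On both readings the larger model holds cognitive style and the null model does not. Neither reading reveals how much of the simulated signal came from style and how much from gabapentin interactions.

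**The case against.** The strongest reply concerns section 11. Power depends on the alternative simulated as well as on the test, and the only alternative described there is a three-way interaction. Had the signal lain wholly in the gabapentin interactions, a noncentrality of 23.02, which gives 90% on 14 df, would give about 97% on 6 df, so the >90% would be conservative for the worded H_1. Section 8's symbolic H_1 is also the overall contrast, and the >90% may be correct for it. This stands. A reader might infer that the >90% is not power for H_1, or that the trial is underpowered for the interactions. The SAP supports neither: the simulated effects are not given, and the figure of expected differences is missing from the text at hand.

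A second reply is that section 17 has each term examined after a significant result, so a style-only finding would generally come to light. That lowers the risk. But section 27 does not make its conclusion wait for those tests, and section 17 does not say which of them must be positive.

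Third, a hypothesis about gabapentin could be isolated on 2 df (three-way only), 6 df (its interactions) or 8 df (all its terms), and the primary objective also covers gabapentin's effectiveness as such. The choice is open to debate. Six degrees of freedom fits the worded H_1 most closely, since that speaks of a group difference dependent on the interactions.

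**Conclusion.** The section 27 conclusion is wrong as written. Rejecting m_0 does not show that an interaction matters, because m_0 lacks all three main effects. That follows from the model definitions and needs no assumed effect. Section 8 carries the same inconsistency between its worded and symbolic H_1.

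The size does depend on assumptions: an effect of style on the intercept only, log(time) or linear form, complete data and an assumed r. Under these, false support for the interaction hypothesis ranges from 13% at r = 0.1 to 99.8% at r = 0.4, and passes 90% when style explains about 8.8% of between-patient variance in the intercept.

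For section 11 the conclusion is narrower: the text does not establish whether the >90% is power for the worded H_1.

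**What to change.** In section 27, keep the m_0 against m_1 test as the gate. Make the statement of support for the primary hypothesis depend on a second nested comparison: m_0 plus the three main effects and style × pupil, against m_1. This tests the three gabapentin interaction terms, 6 df with log(time). Bring the worded and symbolic H_1 in section 8 into line with it. Section 14 dates completion of the primary analysis to March 2023, so label the comparison as added later.

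In section 11, say that the >90% refers to the overall comparison. If the simulation behind it also gives power for the 6-df comparison, state that figure with the effects assumed.

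The cost is one extra model fit on existing data and a few sentences; N and m_1 do not change. The price is that a significant overall test would no longer be enough to support the gabapentin interaction claim.
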